10.7. Quality Control and Quality Assurance

The Sponsor or designee will conduct periodic visits or audits during or after the study to ensure that the protocol and GCP are being followed. The monitors may review the drug storage area, study drug stocks, drug storage/accountability/disposition records, source documents, and regulatory documentation. The Investigator and institution will permit direct access to the physical spaces, records, and source documents to perform this verification to the Sponsor or designee monitors/auditors, IRB members, and appropriate regulatory authority inspectors.

The Investigator must immediately notify the Sponsor or its designee of any regulatory inspection notification, will cooperate with the Sponsor or designee to prepare the study site for the inspection, will be present during the inspection along with relevant study staff, will allow the Sponsor or designee to be present during the inspection, and will provide copies of any inspection findings.

10.8. Financial Disclosure

Investigators and sub-investigators will provide the Sponsor with sufficient, accurate financial information as requested to allow the Sponsor to submit complete and accurate financial

certification or disclosure statements to the appropriate regulatory authorities. Investigators are responsible for providing information on financial interests during the course of the study and for 1 year after completion of the study.

11. ETHICS

11.1. Ethical Conduct of the Study

The study will be conducted in accordance with legal and regulatory requirements, as well as the general principles set forth in the International Ethical Guidelines for Biomedical Research Involving Human Subjects (Council for International Organizations of Medical Sciences 2002), ICH GCP Guidelines, and the Declaration of Helsinki (World Medical Association 1996 and 2008).

In addition, the study will be conducted in accordance with the protocol, ICH GCP, and applicable local regulatory requirements and laws.

11.2. Written Informed Consent

An informed consent form (ICF) meeting the requirements of 21 CFR §50, local regulations, ICH guidelines, Health Insurance Portability and Accountability Act (HIPAA) requirements (where applicable), must be reviewed and approved by the Sponsor, approved by the IRB before use, and available for inspection.

The Investigator or authorized representative will explain the nature of the study to the subject and answer all questions regarding the study. Subjects must be informed that their participation is voluntary, and if they choose to participate, will be required to sign the approved ICF. The medical record must include a statement that written informed consent was obtained before any study procedures were performed, along with the date written consent was obtained. The authorized person obtaining the informed consent must also sign the ICF. The original signed ICF will be retained in the Investigator's records, with a copy provided to the subject.

Subjects must be re-consented to the most current version of the ICF during their participation in the study.

11.3. Institutional Review Board/Independent Ethics Committee

The protocol, protocol amendments, ICF, Investigator's Brochure (IB), and other relevant documents (e.g., advertisements) must be submitted to an IRB by the Investigator, and reviewed and approved by the IRB before the study is initiated.

Protocols and any substantial amendments to the protocol will require health authority approval prior to initiation except for changes necessary to eliminate an immediate hazard to study subjects. Any amendments to the protocol will require IRB approval before implementation of changes made to the study design, except for changes necessary to eliminate an immediate hazard to study subjects.

The Investigator will provide written summaries of the status of the study and any other significant safety findings to the IRB annually or more frequently in accordance with its requirements, policies, and procedures. At the end of the study, the Investigator will notify the IRB of the conclusion of the study and its outcome.

12. PUBLICATION POLICY

The Sponsor will comply with the requirements for publication of study results. In accordance with standard editorial and ethical practice, the Sponsor will generally support publication of multicenter studies only in their entirety and not as individual site data.

Authorship will be determined by mutual agreement and in line with International Committee of Medical Journal Editors authorship requirements.

## List of Abbreviations

ADaM	Analysis Data Model
AE	Adverse Event
ATC	Anatomical Therapeutic Chemical
C-SSRS	Columbia-Suicide Severity Rating Scale
CGI-I	Clinical Global Impression – Improvement
CGI-S	Clinical Global Impression – Severity
CRF	Case Report Form
CRO	Contract Research Organization
CS	Clinically Significant
CTQ	Childhood Trauma Questionnaire (CTQ)
ECG	Electrocardiogram
EDC	Electronic Data Capture
EFF	Efficacy Population
EOT	End of Treatment
ET	Early Termination
GAD-7	General Anxiety Disorder (7-item)
HAM-A	Hamilton Anxiety Scale
HAMD-6	Hamilton Depression Rating Scale (6-item)
IB	Investigator's Brochure
ICF	Informed Consent Form
ICH	International Conference on Harmonization
ITT	Intent to Treat
LOCS III	Lens Opacities Classification System III
MADRS	Montgomery-Åsberg Depression Rating Scale
MDD	Major Depressive Disorder
MedDRA	Medical Dictionary of Regulatory Affairs
NCS	Not Clinically Significant
PGI-I	Patient Global Impression of Improvement (PGI-I)

PK	Pharmacokinetics
SAE	Serious Adverse Event
SAF	Safety Population
SAP	Statistical Analysis Plan
SCID-5-CT	Structured Clinical Interview for DSM-5 – Clinical Trials Version
SD	Standard Deviation
SDTM	Study Data Tabulation Model
SF-36	Short Form-Health Survey (36-item)
SOC	System Organ Class
TEAE	Treatment-Emergent Adverse Event
TLF	Tables, Listings, and Figures
WHO	World Health Organization

## **1. Introduction**

EmbarkNeuro is conducting a study to investigate a new treatment for Major Depressive Disorder (MDD). The study background, design and subject assessments for the study are described in the study specific protocol.

The statistical methods to be implemented during the analyses of data collected within the scope of this study will be outlined in this document. The purpose of this plan is to provide specific guidelines from which the statistical analysis will proceed. Any deviations from this plan will be documented in the clinical study report.

## **2. Study Objectives**

### **2.1. Primary Objectives**

The primary objectives of this study are:

- To evaluate the effect of treatment with ANC-501 capsules on depressive symptoms in subjects with MDD
- To evaluate the safety and tolerability of ANC-501 capsules in subjects with MDD

### **2.2. Secondary Objectives**

The secondary objectives of this study are:

- To evaluate effect of ANC-501 at all time points and percent reduction in total symptom scores compared with baseline
- To assess the pharmacokinetic (PK) profile of ANC-501 capsules in plasma using a sparse sampling model

### **2.3. Exploratory Objectives**

The exploratory objectives of this study are:

- To evaluate changes in 12-hour urine, plasma, and saliva cortisol
- To evaluate changes in biometrics
- To evaluate biological samples as potential biomarkers and metabolites
- Patient reported changes in depression and anxiety symptoms

### **3. Study Design**

This is a single-arm, open-label Phase 2 study to assess the safety, tolerability, PK, and efficacy of ANC-501 oral capsules as adjunctive treatment in subjects diagnosed with MDD.

With the exception of subjects permitted to use current stable antidepressant treatment, initiation of psychotropic medications and other medications that may potentially have an impact on efficacy or safety endpoints will not be allowed between screening and completion of the Day 56 assessments. Psychotropic medications, which must have been initiated at least 8 weeks prior to screening, must remain at a stable dose until completion of the Day 56 assessments. During the study, efficacy and safety assessments will be performed. Blood samples will also be collected for PK analysis of ANC-501 and future exploratory biomarker and genetic analysis. A wearable watch-like device will collect data on biometrics, which may be used for exploratory analyses.

Subjects will receive 50 mg ANC-501 Capsules (5  $\times$  10 mg capsules) orally once daily at least 1 hour prior to the morning meal whenever possible for 8 weeks beginning with the first dose administered in the clinic on Day 1 and will return to the clinic for scheduled visits on Days 8, 15, 29, 43, and 56. Follow-up visits will occur on Day 70 and 112. All scheduled visits after Day 1 allow a visit window of  $\pm$  3 days.

Total duration of participation is 20 weeks (up to 30 days screening, 8 weeks dosing, 8 weeks follow-up).

A summary of the schedule of events is provided in Table 1 below.

**Table 1: Schedule of Events**

Study Procedure	Screening Period	Open-Label Treatment Period a							Follow-up Period b	
Visit Days	-30 to -1	Day 1 c	Day 8 (±3 days)	Day 15 (±3 days)	Day 29 (±3 days)	Day 43 (±3 days)	Day 56/ET (±3 days)	Day 70 (±3 days)	Day 112 (±3 days)	
Informed Consent	X									
Demographics	X									
Medical history	X									
Full physical examination	X						X			
Body weight/height/BMI d	X	X								
Vitals e	X	X	X				X			
12-lead ECG		X	X				X			
Safety laboratory tests f	X	X	X				X	X		
Urine drug and alcohol breath test screen g	X	X								
Urine pregnancy test h	X	X								
Hepatitis and HIV serology	X									
Sparse PK blood sampling i		X	X	X	X	X	X			

Exploratory biomarker sampling j		X	X				X		
Genetic sampling k		X							
Ophthalmic exam and LOCS III l	X						X	X	X
SCID-5-CT diagnostic interview	X								
MADRS	X	X	X	X	X	X	X	X	
HAM-A	X	X	X	X	X	X	X	X	
CGI-S	X	X	X	X	X	X	X	X	
C-SSRS m	X	X	X	X	X	X	X	X	
HAMD-6 n		X							
GAD-7 n		X							
SF-36 n		X							
EMAW Orienting Questions n		X							
CTQ	X								
CGI-I			X	X	X	X	X	X	
PGI-I			X	X	X	X	X	X	
SAFER Interview (central rater) o	X								

Inclusion/Exclusion Criteria Review	X	X							
12-hour urine collection for cortisol instructions p	X						X		
Plasma and saliva cortisol sample collection	X						X		
Wearable monitoring instructions and Mobile application training		X							
Continuous Wearable monitoring q		X							
Site download of Wearable data			X	X	X	X	X		
ANC-501 dosing r		X							
ANC-501 Dosing Diary dispensed and reviewed by site		X							
Dispense study medication		X	X	X	X	X			
Adverse events s	X	X							
Prior/Concomitant Medications t	X	X							

Abbreviations: AE = Adverse Event; BMI = body mass index; CGI-I = Clinical Global Impression-Improvement; CGI-S = Clinical Global Impression-Severity; C-SSRS = Columbia-Suicide Severity Rating Scale; CTQ = Childhood Trauma Questionnaire, 28-item; ECG = electrocardiogram; ET = early termination; HAM-A = Hamilton Anxiety Rating Scale; HIV = human immunodeficiency virus; LOCS III= Lens Opacities Classification System III; MADRS = Montgomery-Åsberg Depression Rating Scale; MDD = major depressive disorder; MGH ATRQ = Massachusetts General Hospital Antidepressant Treatment Response Questionnaire; PGI-I = Patient Global Impression of Improvement; PK = pharmacokinetic; SAE = serious adverse event; SAFER = State vs trait, Assessability, Face

and Ecological validity, Rule of 3Ps (pervasive, persistent, and pathological); SCID-5-CT = Structured Clinical Interview for DSM-5 – Clinical Trials Version; HAMD-6= Hamilton Depression Rating Scale (6-item); GAD-7= General Anxiety Disorder (7-item); SF-36 = Short Form-Health Survey (36-item).

- a. Subjects who discontinue study treatment before completing the study and those who prematurely withdraw from the study for any reason should undergo Day 56 visit procedures in-clinic as soon as possible and schedule the Day 70 safety assessments (at +2 weeks post ET visit) and Day 112 follow-up ophthalmic visit (at +8 weeks post ET visit).
- b. Subjects will return to the site on Day 70 and 112 for a follow-up visit.
- c. Day 1 procedures are to be completed prior to dosing, except for sparse PK sampling which will be performed prior to dosing and between 0.75 and 2 hours post-dose.
- d. Body weight and height will be measured at screening and BMI will be calculated. Only body weight and BMI calculation will be performed at subsequent visits.
- e. Vital signs include oral temperature (°C), respiratory rate, heart rate, and blood pressure (supine and standing).
- f. Safety laboratory tests will include hematology, serum chemistry, coagulation, and urinalysis.
- g. Urine toxicology for selected drugs of abuse (barbiturates, amphetamines, cocaine, opioids, cannabis) and breath test for alcohol.
- h. Urine pregnancy test will be conducted only in female subjects of childbearing potential. Female subjects who prematurely discontinue will have a pregnancy test performed at the ET visit.
- i. A blood sample for sparse PK sampling will be collected pre-dose and between 0.75 and 2.0 hours post-dose at the Day 1 visit, and between 0.75 and 2.0 hours post-dose at all other indicated visits whenever possible (with date/time of previous dose provided by the subject).
- j. A blood sample for exploratory biomarker analysis will be collected in conjunction with PK sampling on Days 1 (pre- post-dose), 8, and 56.
- k. A genetic sample (blood) for exploratory biomarker testing will be collected before the first dose of drug.
- l. Ophthalmic exam, including slit-lamp imaging, may be performed by an appropriately trained and qualified individual as delegated by the PI and documented in the Study Delegation Log. However, a licensed ophthalmologist or optometrist must oversee this work and will make the determination on subject eligibility as per inclusion criteria #4. Slit lamp imaging of the lens of both eyes will be taken and sent to a central reader for assessment using the LOCS III. Ideally the exam would be performed after cortisol results are known and the subject is otherwise deemed eligible to continue with screening assessments. Additional slit lamp imaging of the lens of both eyes may be performed during the treatment period and sent to a central reader for assessment using the LOCS III, per Investigator's discretion.
- m. The “Baseline/Screening” C-SSRS form will be completed during screening. The “Since Last Visit” C-SSRS form will be completed at any time of day at all subsequent time points.
- n. The Short Form-Health Survey (36-item) (SF-36) weekly. The Hamilton Depression Rating Scale (6-item) (HAMD-6) and the General Anxiety Disorder (7-item) (GAD-7) will be completed up to twice a day for a minimum of three days per week (to achieve 6 collections per week). Subjects will answer EMA orienting questions up to three times per day in conjunction with the other assessments being collected via the EMA application on their cell phones or the provided device.
- o. Conducted by central reader after Screening visit, but prior to Day 1 visit. The MADRS, MGH ATRQ and confirmation of MDD will be conducted by central rater for determination of eligibility.
- p. Study site personnel will dispense equipment and train subjects on 12-hour urine collection for measuring cortisol level. At the Day 43 visit, study site personnel will dispense equipment and retrain subjects on the 12hour urine collection to measure cortisol levels (the collection will be returned to the site at the Day 56 visit). On Day 54, the site will contact the subject to remind them to begin collection on Day 55.
- q. Subjects will wear their wearable watch-like device throughout the day and night except when charging.
- r. At the Day 1 visit, subjects confirmed as eligible will receive a 50 mg dose of study drug at the study site prior to eating. All other doses will be taken by the subjects at home

- s. All AEs will be recorded from study drug administration on Day 1 until Day 112visit. Serious adverse events that occur subsequent to the signing of the informed consent (i.e., during the Screening Period) as a result of study participation will be recorded, as well as all SAEs occurring from study drug administration on Day 1 until Day 112 visit.
- t. Includes medications taken within 30 days prior to informed consent and throughout the study

## 4. Analysis Populations

**Safety Population (SAF):** The Safety population will consist of all subjects who received at least one dose of ANC-501. This population will be used for all Safety analyses.

Enrolled Subjects: The date the first dose of ANC-501 is administered is the date a subject is considered enrolled into the study. Enrolled subjects and the safety population are equivalent.

**Efficacy Population (EFF):** The Efficacy population will consist of all subjects who received at least one dose of ANC-501 and have completed treatment. This population will be used for all Efficacy analyses.

EFF differs from the protocol due to two subjects who were discontinued near the beginning of the study due to a failed Day 1 drug screen.

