1.2. Study Schema

1.3. Schedule of Events

Study Procedure	Screening Period		Ope	n-Label Ti	reatment]	Period ^a		Follow-u	ıp Period ^b
Visit Days Window	-30 to -1	Day 1	Day 8 (±3 days)	Day 15 (±3 days)	Day 29 (±3 days)	Day 43 (±3 days)	Day 56/ET (±3 days)	Day 70 (±3 days)	Day 112 (±3 days)
Informed consent	X								
Demographics	X								
Medical history	X								
Full physical examination	X						X		
Body weight/height/BMI d	X	X							
Vitals ^e	X	X	X				X		
12-lead ECG		X	X				X		
Safety laboratory tests ^f	X	X	X				X	X	
Urine drug and alcohol breath test screen ^g	X	X							
Urine pregnancy test h	X	X							
Hepatitis and HIV serology	X								
Sparse PK blood sampling i		X	X	X	X	X	X		
Exploratory biomarker sampling j		X	X				X		
Genetic sampling k		X							
Ophthalmic exam and LOCS III 1	X						X	X	X
SCID-5-CT diagnostic interview	X								
MADRS	X	X	X	X	X	X	X	X	
HAM-A	X	X	X	X	X	X	X	X	
CGI-S	X	X	X	X	X	X	X	X	
C-SSRS ^m	X	X	X	X	X	X	X	X	
HAMD-6 ⁿ		4							
GAD-7 ⁿ		•							

Study Procedure	Screening Period	Open-Label Treatment Period ^a						Follow-up Period ^b	
Visit Days Window	-30 to -1	Day 1	Day 8 (±3 days)	Day 15 (±3 days)	Day 29 (±3 days)	Day 43 (±3 days)	Day 56/ET (±3 days)	Day 70 (±3 days)	Day 112 (±3 days)
SF-36 ⁿ		4					-		
EMAW Orienting Questions ⁿ		4					•		
CTQ	X								
CGI-I			X	X	X	X	X	X	
PGI-I			X	X	X	X	X	X	
SAFER Interview (central rater) °	X								
Inclusion/Exclusion Criteria Review	X	X							
12-hour urine collection for cortisol instructions ^p	X						X		
Plasma and saliva cortisol sample collection	X						X		
Wearable monitoring instructions and Mobile application training		X							
Continuous Wearable monitoring q		4					•		
Site download of Wearable data			X	X	X	X	X		
ANC-501 dosing r		•					•		
ANC-501 Dosing Diary dispensed and reviewed by site		-					-		
Dispense study medication		X	X	X	X	X			
Adverse Events s	X	←							→
Prior/ConcomitantMedications t	X	←							—

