7. DISCONTINUATION OF STUDY TREATMENT AND SUBJECT WITHDRAWAL

7.1. Discontinuation of Study Treatment

A subject must be discontinued from study treatment for any of the following:

- 1. Unacceptable toxicity, despite maximal supportive care and/or dose reduction.
- 2. Subjects exhibiting a change in the LOCS III greater than or equal to 0.5 in Nuclear Opalescence, Cortical Opalescence or Posterior Subcapsular Opalescence in either eye or clinically significant eye changes (e.g., incident of cataract).
- 3. Investigator decision (may include the need for antidepressant therapy or other therapy not otherwise permitted in the study, including ECT or changes to cognitive/behavioral psychotherapy) or noncompliance with study requirements.
- 4. Subject becomes or intends to become pregnant.
- 5. Subject withdrawal of consent for further study treatment.
- 6. Study termination by the Sponsor.

Subjects discontinuing treatment should complete the Early Termination visit procedures and enter the Follow-up Period.

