9.3. Analysis Populations

For the purposes of analysis, the following populations are defined:

Table 5: Definitions of Analysis Populations

Analysis Population	Definition
Safety	Includes all subjects who received at least one dose of ANC-501. This is the primary population for exposure and safety analyses.
Efficacy	Includes all subjects who received at least one dose of ANC-501 and have at least one post-baseline efficacy evaluation. This is the primary population for efficacy endpoints.

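### SAP Section 4 limits the Efficacy Population to treatment completers, a rule much wider than its stated reason of two failed Day 1 drug screens

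*SAP*

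**What the plan says.** The two documents define the Efficacy Population differently.

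- **Protocol 9.3, Table 5:** "Includes all subjects who received at least one dose of ANC-501 and have at least one post-baseline efficacy evaluation". The table names this as the primary population for efficacy endpoints.
- **SAP Section 4:** "The Efficacy population will consist of all subjects who received at least one dose of ANC-501 and have completed treatment". Sections 4 and 8 both apply this set to all efficacy analyses.

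The SAP attributes the difference to "two subjects who were discontinued near the beginning of the study due to a failed Day 1 drug screen". SAP Section 11 makes the SAP prevail over the protocol, and no analysis on the protocol population is planned.

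Other provisions bear on the point:

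- SAP Table 1, footnote c: "Day 1 procedures are to be completed prior to dosing, except for sparse PK sampling". The Day 1 drug screen is therefore a pre-dose check.
- SAP Table 1, footnote a: subjects who stop early "should undergo Day 56 visit procedures in-clinic as soon as possible". Those procedures include the MADRS.
- Protocol 7.1 lists reasons for stopping treatment, among them "Unacceptable toxicity, despite maximal supportive care and/or dose reduction" and "Investigator decision (may include the need for antidepressant therapy".
- SAP 5.1 imputes no efficacy values. SAP 8.3.2 and 8.3.3 compute responder and remitter percentages only over subjects measured at the visit.
- SAP 5.2 does not define completion of treatment.

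**The concern.** Completing treatment is something that happens after baseline and may depend on how the subject is doing. A population defined by it is selected on a possible consequence of treatment. In a randomised trial the control arm would give some check on this. Here there is none: the mean MADRS change at Day 56, with its confidence interval and p-value (SAP 8.2.1), and the responder and remitter rates are the whole efficacy result. If subjects who stop early do worse, a completer-only analysis overstates benefit.

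The stated reason does not call for such a rule. It concerns two identified subjects and a check made before the first dose.

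**Working it through.** The plan has no figure of its own to reproduce. The sample size of up to 20 was set on clinical grounds, with no assumed effect, SD or dropout rate. The check is a comparison of texts followed by an illustration of size.

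**1. Does the reason need the rule?** There are two cases, and the documents do not say which applies.

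- If the two subjects had no post-baseline efficacy evaluation, the protocol definition already leaves them out.
- If they had one, an exclusion for a failed pre-dose drug screen removes exactly those two.

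Neither case requires a completer rule.

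**2. Who else is removed?** Anyone who stops treatment early for any reason in protocol 7.1: toxicity, LOCS III change, investigator decision, pregnancy or withdrawn consent.

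**3. Which data go unused?** The MADRS is scheduled at Days 8, 15, 29, 43, 56/ET and 70. Under the SAP rule, none of a stopper's scores enter the SAP's efficacy summaries, including those taken while on drug.

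**4. At which visits does the rule act?** Two effects need to be kept apart.

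- (a) At visits where a stopper was measured, the population rule alone changes the summary.
- (b) At Day 56, a stopper with no score would be absent under the protocol population too, because nothing is imputed and the denominators count only measured subjects. The population rule matters there only if the stopper has a Day 56 score or the early-termination (ET) score counts as Day 56. The schedule puts Day 56 and ET in one column, but the SAP gives no mapping rule.

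**5. Illustration of size.** From the documents: at most 20 enrolled, less the two drug-screen failures, gives 18. Assumed: d further stoppers (0 to 4), 8 responders and 5 remitters who are all completers, and a gap g of 0 to 15 MADRS points in mean improvement between completers and stoppers.

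Responder rate among completers = 8/(18 − d). With stoppers kept and counted as non-responders it is 8/18 = 44.4%. The difference between these two equals the population effect alone only if every stopper was measured at that visit and none responded.

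Shift in mean change = (d/18) × g, if all stoppers are measured.

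| d | Completers | Responders | Mean shift, g = 5 | g = 10 | g = 15 |
|---|---|---|---|---|---|
| 0 | 18 | 8/18 = 44.4% | 0 | 0 | 0 |
| 1 | 17 | 8/17 = 47.1% | 0.28 | 0.56 | 0.83 |
| 2 | 16 | 8/16 = 50.0% | 0.56 | 1.11 | 1.67 |
| 3 | 15 | 8/15 = 53.3% | 0.83 | 1.67 | 2.50 |
| 4 | 14 | 8/14 = 57.1% | 1.11 | 2.22 | 3.33 |

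With g = 0 the shift is zero for any d. For remitters the completer rate runs from 5/18 = 27.8% to 5/14 = 35.7%, against 27.8% with stoppers kept. With d = 4, up to 4/18 = 22.2% of the scores at an early visit would go unused.

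**6. Direction.** It can reverse. If 2 of 4 stoppers were among the 8 responders at their ET visit, the completer rate is 6/14 = 42.9%, against 8/18 = 44.4% with ET scores counted.

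**The case against.** The best defence is that the effect may be nil. SAP Section 4 puts the whole difference down to two subjects and was written after they had stopped, so it can be read as saying that nobody else is affected. Restoring the protocol population might not change the observed Day 56 mean. The 44.4% comparator relies on counting stoppers as non-responders, a convention in neither document, and the other inputs are assumed. The study is small, open-label and without formal hypothesis testing under protocol 9.1. The change is disclosed and, by SAP Section 5, precedes database lock. SAP 7.1 reports both population sizes and the reasons for stopping. SF-36, HAMD-6 and GAD-7 analyses are left to separate plans that are not available.

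Much of this stands. The realised effect is unknown and could be zero or of either sign, the figures are illustrative, and the reach into the separate plans cannot be checked. Counting subjects without a score as non-responders is one convention among several.

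It does not rescue the rule. If only two subjects are meant, the text should say so, and as written it excludes every non-completer. Disposition tables show how many subjects were dropped but do not correct the estimates. Disclosure does not make a reason that covers two subjects justify a rule that covers all early stoppers.

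**Conclusion.** The concern holds. SAP Section 4 departs from protocol 9.3 for the primary efficacy endpoint, the stated reason does not support the rule adopted, and the rule discards scores that the protocol arranges to collect. This should be corrected.

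Overstatement of benefit is the expected direction, but it is not shown. On the assumptions above the responder rate rises by 0 to 12.7 percentage points (57.1 − 44.4) and the mean change shifts by 0 to 3.3 MADRS points for 0 to 4 further stoppers. These shifts apply at visits where stoppers were measured, and at Day 56 only if they have a score there or ET scores count. The effect is zero if only the two drug-screen failures stopped, or if stopping is unrelated to outcome.

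**What to change.** 1. Restore the protocol 9.3 population in SAP Section 4. If the two subjects are to be left out, exclude them by a rule based on the failed pre-dose Day 1 drug screen, not on completion.
2. State how ET scores and missing Day 56 scores enter the Day 56 mean change.
3. Report Day 56 responder and remitter percentages over all Efficacy Population subjects, counting those without a Day 56 score as non-responders and non-remitters.
4. Keep the completer analysis as a labelled supplementary table, and define completion of treatment in SAP 5.2.

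Steps 2 and 3 are needed because step 1 alone may leave the Day 56 results unchanged. If another convention is preferred in step 3, it should be named and applied to the same denominator.

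The cost is SAP wording and one or two tables, with no new data. The headline figures may become less favourable, or may not move if nobody else stopped early.
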